8 PATIENT COMPLETION AND WITHDRAWAL

8.1 Patient Completion

Any patients who are continuing to receive study drug at the time of final data cut-off (i.e., those who have not previously withdrawn) will be deemed as having completed the study.

If a patient withdraws from the study during the treatment period, every attempt should be made for the patient to attend the safety follow-up visit, which will represent the end of the patient's participation in the study, and to provide information of survival status. If the patient does not agree to have the safety follow-up, only survival data will be collected. The last clinic visit will be considered the final study visit for the patient (i.e., the patient completion/withdrawal date). If a patient refuses a safety follow-up visit after withdrawing from the study, the last contact date with the patient will define the patient completion/withdrawal date.

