9.1.3 Adverse Event Reporting

The Investigator, or authorized designee, should regularly ask the patients how they are feeling to encourage AE reporting. The person approaching the patients should use a non-leading question such as “How are you feeling?”.

All observed or volunteered AEs, regardless of suspected causal relationship to study drug, will be recorded on the AE page(s) of the eCRF.

In addition, abnormal objective test findings (e.g., ECG changes, abnormal laboratory test results) that result in a change in the study drug dosage or in discontinuation of the drug, or require intervention or diagnostic evaluation to assess the risk to the patient, should be recorded as AEs. Clinically significant changes in physical examination findings and objective test findings should also be recorded as AEs.

Study Number: ONO-7475-01 Protocol	Version: 10.0 [incorporating Amendments #1–9]
--	--

Adverse events will be collected from the time informed consent is given until the patient has completed the study.

Any AEs that are ongoing at the time the patient completes the study will be followed by the Investigator until the AEs are resolved, the patient's condition is stable or persistent, the patient's death, or until the patient is lost to follow-up. Any pregnancies reported after completion of the study must also be reported as per Section 9.2.5.

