9.2.2 Serious Adverse Event Reporting by the Investigator or Designee

All SAEs, regardless of suspected relationship to study drug, must be reported by the Investigator or their authorized designee to designated service provider immediately, and in no case later than 24 hours, following knowledge of the SAE.

All SAEs are documented in the SAE form and reported electronically through the designated service provider's electronic data capture (EDC) system.

If the event meets serious criteria and it is not possible to access the EDC system, the Investigator or their authorized designee should contact the designated service provider, either by e-mail or telephone, and fax the completed paper SAE form to the designated service provider within 24 hours of awareness. The SAE

information must be entered into the EDC system within 24 hours of the system becoming available.

Safety Contact Information

[REDACTED]

[REDACTED]

[REDACTED]

[REDACTED]

[REDACTED]

The initial report of an SAE must not be delayed by the investigational site beyond 24 hours in order to collect additional information. Any medical information relevant to the reported SAE which becomes available to the investigational site staff following the initial SAE report should be reported to designated service provider as part of a follow-up SAE report. The reporting procedure should be referred to the outlined above for initial reporting of SAEs. Medical records transmitted as part of the SAE report must not disclose study patients' personal data, such as patient name, any contact information, name of patients' relatives, etc. The study patient is to be identified by the unique study-specific subject number only.

As for AEs, SAEs will be collected from the time informed consent is given until the follow-up visit, or until voluntary withdrawal of a clinical study patients' consent (refer to Section 8.3). SAEs that occur after the SAE reporting period and that are considered related to study drug will be reported to the Sponsor, if the Investigator becomes aware of them.

Unless they withdraw consent for further follow-up, patients who discontinue study therapy will be followed for acquisition of safety information through 30 days after the last dose of study treatment (or initiation of new anti-cancer therapy, whichever occurs first), and for collection of information regarding survival.

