10.2.2.4 Safety Analyses

The SAF will be used for all safety analyses by default.

Safety will be evaluated by monitoring all AEs and SAEs.

All AEs will be tabulated and graded according to NCI CTCAE version 4.03 for each patient cohort. Verbatim descriptions of AEs reported during the study period will be mapped to Medical Dictionary for Regulatory Activities (MedDRA) preferred terms and body systems.

Treatment-emergent AEs are defined as:

- Any AEs with an onset date on or after the study drug start date and no later than 30 days after permanent discontinuation of study drug (or initiation of new anti-cancer therapy, whichever occurs first)

All treatment-emergent AEs will be summarized in frequency tables.

For any AE summary showing the AEs by NCI CTCAE grade, the highest grade will be used for those AEs that occurred more than once in an individual patient during the study.

The DLTs will be summarized in frequency tables and also listed.

Laboratory safety assessments will include regular, routine monitoring of hematology and blood chemistry, and urinalysis.

Laboratory data collected during the study will be analyzed and summarized using both quantitative and qualitative methods. Summaries of laboratory data will be provided and will include data collected up to the last dose of study drug plus 30 days for patients who have permanently discontinued study drug.

Laboratory NCI CTCAE grades at baseline and worst post baseline will be summarized in shift tables.

Body weight and vital signs and their change from baseline will be summarized.

Descriptive statistics will be used to summarize ECOG performance status.

A summary of ECG parameters will be provided for each scheduled time point and categorical summaries of maximum observed and change from baseline values will be presented for QTcF.

Prior and concomitant medications will be summarized.

Full details will be provided in the SAP.

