11.5 Data Management

Data management for all study data will be conducted by Medpace designated staff.

An EDC system [REDACTED] will be used to collect data for this study. Trained Investigator site staff will enter the data required by the protocol into the EDC system by completing an eCRF from source documents (e.g., medical records and study-specific data capture tools as needed). All information in the eCRFs must be traceable to these source documents. Data management processes will be described in a Data Management Plan (DMP). The DMP will be reviewed and approved by the Sponsor and made final prior to study start.

The EDC system will keep track of all data entry, alterations, and query resolution in an audit trail. The audit trail will form an integral part of the application and will be archived alongside the data.

Automatic validation programs within the EDC system will check for data discrepancies during and after data entry and, by generating appropriate error messages, allow the data to be confirmed or corrected online by the designated site staff. The system will keep track of all data entry, alteration, and query resolution via an audit trail. The Investigator must certify that the data entered are complete and accurate by provision of an electronic signature for each eCRF. If any changes are made to the eCRF after a form has been locked and electronically signed, the Investigator will be required to repeat the electronic signature process to authorize agreement with any new information or changes.

After database lock, the Investigator will receive copies of the patient data for archiving at the investigational site. The data will also be extracted and provided to the Sponsor.

The majority of the data will firstly be recorded onto source documents and the Investigator will be required to complete an Investigator source agreement at the site initiation visit where the source, location, and type of source will be agreed with the Investigator and documented. Other data will be handled and processed as follows:

- Medical history and AEs will be coded using the MedDRA terminology
- Concomitant medications will be coded using WHO Drug dictionary. Concomitant (non-drug) therapies will be coded using MedDRA (same as medical history and AEs)
- Safety laboratory samples will be processed locally and the results entered into the eCRF
- PK and biomarker samples will be processed centrally and the results sent electronically to Medpace

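### Laboratory summaries have no cut-off at new anti-cancer therapy, although treatment-emergent adverse events in the same section do (minor)

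*Combined protocol and SAP*

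**What the plan says.** Section 10.2.2.4 counts an adverse event as treatment-emergent if its onset is on or after the first dose and "no later than 30 days after permanent discontinuation of study drug (or initiation of new anti-cancer therapy, whichever occurs first". A few lines later, the same section says that laboratory summaries "will include data collected up to the last dose of study drug plus 30 days for patients who have permanently discontinued study drug". It adds: "Laboratory NCI CTCAE grades at baseline and worst post baseline will be summarized in shift tables". Neither laboratory sentence mentions new therapy.

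Four other sections bear on which values reach the database:

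- Section 9.2.2: patients who stop study therapy are "followed for acquisition of safety information through 30 days after the last dose of study treatment (or initiation of new anti-cancer therapy, whichever occurs first".
- Section 8.1: after withdrawal during treatment, "every attempt should be made for the patient to attend the safety follow-up visit". New therapy is not mentioned.
- Section 9.1.3: "Adverse events will be collected from the time informed consent is given until the patient has completed the study". Again, new therapy is not mentioned.
- Section 11.5: "Safety laboratory samples will be processed locally and the results entered into the eCRF".

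Section 10.2.2.4 leaves full details to the SAP. The document available for review contains no SAP text that settles the laboratory window.

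**The concern.** The adverse event rule separates what happens on study treatment from what happens on the next treatment. The laboratory rule does not make that separation, and nothing in the plan explains the difference. The laboratory sentence is also the exception within the plan: safety follow-up in Section 9.2.2 and best overall response in Section 10.2.2.1 both stop when other anti-leukemic or anti-cancer therapy begins.

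A worst-grade table is sensitive to a single value. One blood count taken after a patient starts another myelosuppressive regimen is enough to fix that patient's cell in the shift table. The study is open label and non-randomized (Section 3.5), so no control arm would carry the same distortion. The laboratory tables and the treatment-emergent tables could then disagree for reasons unrelated to the study treatment.

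**Working it through.** The plan gives no figure to reproduce, so the check compares the two windows and works out the gap between them.

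**Inputs.** Both windows come from Section 10.2.2.4. Let t be the number of days from last dose to the start of new therapy, and take permanent discontinuation and last dose as the same day. The documents give no distribution for t, so the values used below are assumptions.

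**Formulas.**

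- Adverse event window after last dose: min(30, t) days.
- Laboratory window after last dose: 30 days.
- Excess laboratory window: 30 − min(30, t) days.

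**Results.**

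- t = 7: 30 − 7 = 23 days of possible laboratory data beyond the adverse event cut-off.
- t = 14: 30 − 14 = 16 days.
- t = 21: 30 − 21 = 9 days.
- t of 30 or more: 0 days; the two rules agree.

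**Illustration (hypothetical patient).** Last dose is on day 40 with Grade 2 neutropenia, new therapy starts on day 45, and a count on day 65 shows Grade 4. The adverse event window closes on day min(40 + 30, 45) = 45. The laboratory window closes on day 40 + 30 = 70. Day 65 lies inside the second window and outside the first. If the count is in the database, the shift table shows Grade 4, while a neutropenia event with onset on day 65 is not treatment-emergent.

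**Can such a value reach the database?**

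- Section 9.2.2 points to no. It ends follow-up for safety information at new therapy, and Section 5.9 lists clinical laboratory tests among the safety assessments.
- Sections 8.1 and 11.5 leave room for yes. The safety follow-up visit is sought after withdrawal with no stated lapse at new therapy, and local results are entered in the eCRF.
- The Part D visit schedule, which could show whether blood is drawn at that visit, is not visible in the public document.

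**Weight of one patient.** If all 47 planned Part D patients are pooled, one affected patient moves one row by 1/47 = 2.1 percentage points, and by more within a dose level. This is the weight of a single patient, not an estimate of how many are affected.

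**The case against.** The strongest defence is Section 9.2.2. Safety information naturally includes laboratory tests, so planned laboratory follow-up would end at new therapy. In the illustration, the day-65 count would not be collected under the plan. The laboratory sentence only limits data that have been collected, and the SAP, which must be approved before database lock (Section 10.2.4), may set the window. Much of this stands, and it can bring the problem down to nothing in practice. It does not remove it. Section 9.2.2 is a follow-up rule placed in the section on serious adverse event reporting, not an analysis filter, and Section 8.1 carries no matching limit. If Section 9.2.2 does govern, the laboratory sentence is out of line with it and should still be corrected.

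A reader might infer four stronger points that the documents do not support:

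- *That the plan sets out to summarise laboratory data after new therapy.* It does not say so. It states an inclusion window that does not address new therapy.
- *That post-switch cytopenias would be reported as ONO-7475 toxicity.* Shift tables carry no attribution. Relationship is assigned to adverse events only (Section 9.1.2), and in Part D the tables describe ONO-7475 plus venetoclax.
- *That these tables are the direct check on the statement in Section 1.3 about ONO-7475 and venetoclax pancytopenia.* Part D has no venetoclax-alone arm, so they cannot isolate the contribution of ONO-7475 under either window.
- *That the effect can be given as a percentage.* The documents give no rate of switching within 30 days, no rate of sampling after a switch, and no proportion of worst grades set by such a sample. Patients already at Grade 4 on study would not be affected.

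**Conclusion.** The inconsistency is real and minor. Section 10.2.2.4 cuts treatment-emergent adverse events at new anti-cancer therapy and does not cut laboratory data there, so the laboratory window can run up to 30 − t days longer for a patient who switches t < 30 days after last dose. Any value entered in that interval can contaminate the descriptive summaries and the worst-grade shift tables and put them at odds with the treatment-emergent tables.

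The number of patients affected cannot be derived. It is small or zero if Section 9.2.2 is applied to laboratory sampling. The conclusion rests on a literal reading of the laboratory sentence and on there being no SAP text in the available document that sets another window. Error rates, power and sample size do not depend on it.

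**What to change.** In Section 10.2.2.4 and the SAP, keep the limit of 30 days after last dose in the laboratory sentence and add the clause that the section already uses for adverse events: "or initiation of new anti-cancer therapy, whichever occurs first". State that the worst-post-baseline grade in the laboratory shift tables is taken from the same window. Show any later values in listings.

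Reconcile Sections 8.1, 9.1.3, 9.2.2 and 10.2.2.4 so that it is clear what is collected after new therapy starts and what is summarised. The change need not extend to vital signs, ECG or ECOG status on this ground, because the section states no post-treatment window for them.

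The cost is one clause and one date filter. The start date of new therapy is already needed for the adverse event rule. The downside is that a few late values move from tables to listings; no data are lost.

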10.2.3 Interim Analysis (Part D only)

All interim analyses will be assessed by the SRC for Part D as described in Section 11.7 (further details are given in the SRC Charter) with the purpose of providing recommendations to the Sponsor.

10.2.3.1 Safety Assessment Group Analysis

The SA group analysis will be performed when each cohort has the required number of DLT evaluable patients. The analysis will include all patients in the SAF and will include safety and PK data. No formal efficacy testing or analysis will be performed at this point.

10.2.3.2

10.2.4 Reporting Deviations from the Statistical Analysis Plan

The SAP will be approved prior to the database lock on Part A for Part A analysis. For Part D, the SAP will be reviewed and updated based on the emerging data from Part A accordingly but updates will be approved prior to database lock for Part D. Any deviations from the SAP will be described in the CSR.

11 STUDY ADMINISTRATION

11.1 Regulatory and Ethical Considerations

11.1.1 Regulatory Authorities

Approval from the Regulatory Authorities will be obtained prior to study-specific screening of the first patient, according to applicable national and international regulations and guidelines.

11.1.2 Institutional Review Board

Before initiating the trial, the Investigator must have written and dated approval from the IRB for the trial protocol, the written informed consent form, consent form updates, and any other written information to be provided to the patients. As part of the Investigator's written application to the IRB, the Investigator must provide the IRB with a current copy of the IB. If the IB is updated during the trial, the Investigator must supply a copy of the updated IB to the IRB.

The Investigator is required to obtain approval from the IRB if changes to the protocol, written informed consent form, written information to be provided to the patients and/or other documents are classed as substantial amendments.

The Investigator is required to report promptly to the IRB any new information that may adversely affect the safety of the patients or the conduct of the trial.

If required by local regulations the Investigator should submit written summaries of the trial status to the IRB on an annual basis and upon completion of the trial, the Investigator should complete and send the End of Trial Notification form.

11.1.3 Protocol Adherence

The protocol must be read thoroughly and the instructions followed exactly. Any deviations should be agreed by both the Sponsor and the Investigator and where appropriate, written protocol amendments will be made to reflect the changes agreed upon. Where a deviation is necessary for the well-being of a patient, the ONO Medical Officer must be informed of the action as soon as possible and amendments submitted to IRB.

A protocol amendment requires IRB and regulatory approval if it constitutes a substantial amendment.

In the event that an unexpected and extended situation which impacts on study conduct develops (e.g., a public health emergency such as a pandemic disease), certain protocol deviations may be unavoidable. In this circumstance, any protocol deviations must be recorded along with the specific reason for the deviation as per usual practice but additional information must be recorded regarding the root cause of the issue (e.g., pandemic disease) and the Sponsor will consider if

alternative study procedures are required to ensure the patient's safety. Where the Investigator determines a deviation is necessary to maintain patient safety, the Sponsor/Clinical Research Associate or the Medical Monitor must be informed of the action as soon as possible and it must be appropriately documented.

11.1.4 Patient Information and Consent

The Investigator, or person designated by the Investigator, must obtain written informed consent prior to the patient undertaking any study-related activity. The Investigator or an authorized designee must explain the nature of the study and the treatment in such a manner that the patient is aware of his/her rights and responsibilities, as well as potential benefits and risks. The Investigator is also responsible for answering any questions the patient may have throughout the study and for sharing any new information that may be relevant to the patient's willingness to continue his/her participation in the trial in a timely manner.

Patients must also be informed that participation is voluntary and that they may withdraw from the study at any time, without prejudice to their current or future care. Documentation of the discussion and the date of informed consent must be recorded. Once all of their questions have been answered and the patient has voluntarily agreed to participate in the study, patients will be asked to sign and date the informed consent form.

Each patient's original consent form, signed and dated by the patient and by the person who conducted the informed consent discussion, will be retained by the Investigator and a copy will be given to the patient for their records. In obtaining and documenting informed consent, the Investigator must comply with the applicable regulatory requirements and must adhere to GCP and to the ethical principles that have their origin in the Declaration of Helsinki.

11.1.5 Indemnity and Compensation

In the event that it can be demonstrated that a patient suffers any significant deterioration in health or well-being or any harmful susceptibility or toxicity as a direct result of their participation in this study, [REDACTED] will agree to abide by the applicable local guidelines with regard to compensation payable to the patient. The amount of compensation will be calculated by reference to the level of damages commonly awarded in laws of the state in the US for similar injuries at the time when such injury occurred. The Investigator and their employer have insurance cover for the malpractice and/or negligence of their employees and agents.

11.2 Reporting of Urgent Safety Measures

Urgent safety measures may be implemented to protect patients against any immediate hazard to their health and safety. The Investigator must notify the Sponsor immediately (<24 hours) to discuss the hazard and any actions taken or to be taken (if time permits prior to implementation). The Sponsor is required to

Study Number: ONO-7475-01 Protocol	Version: 10.0 [incorporating Amendments #1–9]
--	--

inform the appropriate competent authorities, Investigators and IRBs immediately and in any event no later than 3 calendar days of any urgent safety measures implemented during the study.

